## 1. Protocol

**1.1** Is there a separate, written protocol that will be submitted in addition to this form? (Note: a grant application is not considered to be a protocol)

No

**1.2** Select up to three key words below that best describe this research study:

- Psychology
- Clinical
- Public Health
- Social Work

**1.3** Provide a short summary/abstract of the purpose and procedures of the study proposed in this IRB application.

DO NOT include information on studies not proposed in this application.

Use LAY terminology only. This must be easily understandable by IRB community members and nonscientists.

DO NOT cut and paste technical abstracts from source of support applications that may not be understood by a general audience.

The current application is for regular review of our future intervention that will be developed in year 1 with our partners United Way 211 and Alere Wellbeing Inc.

The future intervention trial will test the effects of two approaches to help low-income smokers quit: a Specialized Quitline and Basic Needs navigation. In low-income populations, basic needs like food, housing, personal safety and money for necessities supersede health needs. We have demonstrated in our previous research that among low-income smokers, those with multiple unmet basic needs are significantly less likely to contact a quitline referral they received, and less likely to remember even getting the referral. But when basic needs problems are resolved, the odds of calling a quitline increase. Addressing basic needs should therefore increase low-income smokers' participation in quit smoking programs. However, those programs will have limited effectiveness if they are not made relevant to economically vulnerable populations. Thus proven approaches like quitlines should be more beneficial when they are adapted to the context and life circumstances of the poor.

Using a 2x2 randomized factorial design, we will compare the effects of Standard and Specialized Quitlines with and without a Basic Needs navigator on smoking cessation among 2000 low-income smokers. The primary study outcome is self-reported 7-day point prevalence abstinence at 6-month follow up. All contacts with participants will be by telephone. This statewide field trial will recruit smokers who call United Way 2-1-1 Missouri. Smokers interested in quitting and joining our study will complete a phone survey and then be referred to the standard or specialized Missouri Tobacco Quitline, provided by Alere Wellbeing, Inc. Both 2-1-1 Missouri and Alere Wellbeing, Inc./Optum are research partners in this study. Embedding the study in these practice agencies will accelerate the path to application should our findings support it.

**1.4** Specify your research question(s), study aims or hypotheses:

Aim 1: Compare the relative and combined effects of Specialized Quitline services and Basic Needs navigation on use of the Missouri Tobacco Quitline by low-income smokers.

Primary research questions:

- What proportion of smokers in each study group enrolls in and receives Quitline services?
- Of those enrolled, does the number of counseling sessions completed vary by study group?
- Of those enrolled, does use of Quitline services (Print, Text2Stop, WebCoach) vary by study group?

Aim 2: Compare the relative and combined effects of Specialized Quitline services and Basic Needs navigation on quit attempts and abstinence among low-income smokers.

Primary research questions (again, by study group):

- What proportion report 7-day and 30-day point prevalence abstinence at 3 and 6 months?
- What proportion report quitting smoking for at least 24 hours (i.e., make a quit attempt)?
- What proportion report using any pharmacologic cessation aids, like nicotine replacement?

Aim 3: (Dissemination and Implementation Aim) Conduct scalability and economic evaluations to assess the sustainability of the study's referral and intervention approaches.

Primary research question (again, by study group):

A. What are the costs and benefits of each study condition per Quitline referral, per smoker interaction with the Quitline, and per successful quitter from the perspective of Quitline funders and providers?

**1.5** Background and significance and/or Preliminary studies related to this project:

There is a greater burden of smoking and smoking-related cancers in low-income populations.

Compared to other Americans, those with lower incomes are more likely to smoke (27.9% prevalence in 2012), have greater nicotine dependence, lower readiness to change, lower self-efficacy for quitting, are less likely to know about and use evidence-based methods to quit smoking, and less likely to quit. Smoking-related cancers disproportionately affect the poor and uninsured and those with less than a high school education. Smoking deepens poverty among poor populations.

In addition to the health consequences of smoking, it is increasingly clear that low-income smokers and their families suffer greater financial hardship because of tobacco use. The prioritization of cigarettes over food among low-income smokers has been documented in several studies, and economic analyses show that poor populations spend a greater percentage of income on cigarettes. Low-income smokers and their families experience greater financial stress, food insecurity and a reduced standard of living compared to low-income families with no smokers,

and children in these households have increased rates of malnutrition.

Effective cessation programs and resources are available but underutilized by low-income smokers.

Low-income adults are less likely to know about and use evidence-based methods to quit smoking. While

most Missouri smokers (77%) report knowing about available cessation services, awareness is lower among low income smokers (68%). Proactive telephone counseling for smoking cessation is an evidence-based intervention that is recommended in both clinical and community practice guidelines. Tobacco quitlines provide free telephone counseling, NRT, print information resources, and other support services to help smokers quit. Smokers can call a quitline, or through a third party can consent to be contacted by the quitline (e.g., "fax-back" programs). During an initial quitline contact, smokers arrange a series of phone counseling sessions to be initiated by the quitline (i.e., proactive counseling) and delivered over 1-3 months around a planned quit date. Quitline users who receive NRT are more likely to complete multiple counseling sessions.

Studies show 6-month abstinence rates of 12% among quitline users who receive multi-session counseling, and up to 35% when counseling is accompanied by NRT. Yet only 29% of Missouri smokers report using a cessation medication in their last quit attempt, with an even lower rate (23%) among those with no health insurance. Because quitlines offer population-wide free access to smoking cessation, they have potential to reach a more diverse cross section of American smokers. However, although 65% of current smokers in a national survey knew about tobacco quitlines, only 9% had called a quitline. Studies indicate that the low interest in quitlines is due to smokers' negative perceptions about the service, perceived poor fit of the service, privacy concerns, stigma of using the service and beliefs that they don't need help to quit smoking.

There are unique challenges to promoting smoking cessation in disadvantaged populations. Many low-income smokers have acute needs – no job, inadequate housing, not enough food or money, mental health challenges – that supersede any interest they may have in quitting smoking. It is well established that adults of low socioeconomic status (SES) are less likely to engage in preventive behaviors – including tobacco cessation – than those with higher SES, even after adjusting for employment and insurance status. One explanation is that people living in poverty have such overwhelming needs in other areas of life, that disease prevention becomes secondary to these priorities. Our own data collected from Food Stamps clients showed that unmet basic needs are higher among low-income smokers than among low-income non-smokers. Smokers (n=244) were more likely than non-smokers (n=267) to say they would not have enough money for everyday necessities in the next month (51% vs. 41%, p<.06) and may not have a place to stay for all of the next month (24% vs. 13%, p<.01). In our previous research with low-income 2-1-1 callers, smokers reported more unmet basic needs (M=2.49, SD=1.25) compared to non-smokers (M=2.34, SD=1.24; p=.015).

Novel strategies are needed to increase successful smoking cessation among low-income smokers. Although quitlines are a proven intervention, less is known about how to maximize their use. This is especially true for low-income smokers. For example, while mass media promotional efforts can significantly increase quitline use, some campaigns to promote smoking cessation and quitline use have been less effective in low-education populations. Moreover, time-limited campaigns tend to have short-lived effects. Effective and sustainable approaches are needed to increase quitline use in low-income populations, like building partnerships with systems that already serve them. To date, most efforts to integrate cessation referrals into organizational practice have occurred in health care settings. Lessons learned from these efforts include assuring that: (1) screening and referral is systematic and becomes part of usual care; (2) referrals are made to specialized cessation services, like quitlines; and (3) implementation is monitored carefully and adapted as needed. Additionally, cessation services may be most effective when linked to solutions for smokers' priority problems. For example, worksite health promotion studies among blue collar workers show that when employers address workers' most pressing concerns first (e.g., occupational exposure to hazards), workers become more receptive to other health information provided by the employer and are more likely to participate in smoking cessation and other programs. In our own research with low-income 2-1-1 callers, those who resolved the problem they called about were more likely to contact a health referral for needed prevention services like a mammogram or quitting smoking. Once a problem was resolved, getting additional help from a navigator (vs. no navigator) increased the likelihood of contacting a health referral (45% vs. 27%; p<.05).

Unmet basic needs thwart abilities to address disease prevention and health promotion.

Having unmet basic needs interferes with making behavior changes like quitting smoking. When needs like food, shelter, safety, and money for necessities are unmet, fulfilling them supersedes addressing other life challenges, including modifying unhealthy behaviors. This is not simply a matter of prioritization, but also because scarcity captures the mind in ways that diminish one's cognitive capacity to focus on other goals. This can lead to short term thinking, poor decision making, and reduced awareness of, attention to, or persistence in pursuing resources to resolve the problem.

Low-income individuals also have less access to resources like money, knowledge, power, social support and broad social networks. Those with greater resources have more opportunity to learn about health risks and treatments and take action to reduce risk and minimize the consequences of disease. Having transferable resources allows individuals to adapt to changing social and environmental risks. Thus unmet basic needs are especially harmful if allowed to accumulate. Having unmet basic needs is linked to psychological stress, sleep disturbances, physical and mental health problems, and mortality, and reduces the likelihood of engaging in health promoting behaviors, keeping health care appointments, and using medication as prescribed.

Figure 1 illustrates this process with a proposed pathway from unmet basic needs to health behavior change. The green boxes show where two types of intervention strategies – basic needs interventions (at left) and traditional behavioral interventions (at right) – would typically be delivered. We hypothesize that traditional cognitive behavioral interventions alone will often fail to yield desired results in vulnerable populations because a person's attention, capacity, time, and motivation will have been drained by unmet basic needs. However, when basic needs interventions are also delivered – focused on coping, support, and problem resolution – the odds of health behavior

change occurring should improve. When basic needs are addressed, stress should be reduced or better managed, cognitive bandwidth increased, and ability to attend to, process, and focus on health behaviors increased.

Figure 1. How unmet basic needs undermine health behavior change.

Strong evidence supports this expectation. In well-designed studies, interventions that address basic needs like housing and food have shown beneficial effects on health behaviors, psychological distress, and mental health outcomes like symptoms of anxiety and depression. Our study will compare the independent and combined effects of two intervention approaches that enhance and extend the traditional behavior-focused approach used by evidence-based tobacco quitlines. The first is an adapted, Specialized Quitline service with heightened attention to contextual conditions in the lives of low-income smokers; the second uses navigators to help low-income smokers address their unmet Basic Needs. Both approaches follow the Institute of Medicine recommendations that social science and behavioral research interventions address individuals' health behaviors as well as the socioenvironmental context in which they live. Specific recommendations included: 1) focusing on social and behavioral determinants of health including economics; 2) using of multiple approaches – one size does not fit all; 3) accounting for the special needs of target groups including social class; and 4) engaging social service and other sectors not traditionally involved in health promotion efforts.

**1.6** Literature cited/references (if attaching a grant enter N/A):

Literature cited in attached grant proposal

**1.7** Describe EACH of your participant populations

Include description of any control group(s)

Specify the Inclusion/Exclusion criteria for EACH group

Inclusion criteria: All participants will be recruited from UnitedWay 211 Missouri and must be 18 years and older, English speaking, not in crisis, smoke cigarettes every day of the week, planning to quit smoking in the next 30 days, comfortable receiving calls from smoking expert and project team, willing to provide phone numbers to be reached, Missouri resident, and will be a resident Missouri in the next 3 months

Exclusion criteria: pregnant or planning to pregnant in the next 3 months, insurance through employer, currently breastfeeding, currently enrolled in smoking quitline. The control group, up to 500 participants, will receive standard quit line services and no basic needs navigator.

The treatment groups, up to 1500 participants, will receive either the standard quit line with basic needs navigation, specialized quit line with no basic needs navigation, or the specialized quit line and basic needs navigation.

**1.8** Check all materials/methods that will be used in recruiting participants:

• Telephone script

• Referral

• Medical Records or Other PHI

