The control population will only receive the Standard Quitline (standard of care): Alere's Quit for Life program helps smokers set a quit date within 30 days of enrollment and provides one coaching call before and four carefully timed calls after the quit date to prevent relapse. Calls are scheduled at the smoker's convenience, can be spread over 1-3 months around the quit date, and are adjusted based on the individual's quit success or other needs. Quit coaches try up to five times to reach a smoker for each counseling session. The counseling goal is to increase a smoker's readiness to quit and develop an individually tailored quit plan. In Missouri, Alere provides: (1) up to four sessions of proactive cognitive behavioral counseling by phone from trained quit coaches; (2) access to the same quit coach each call (3) unlimited calls to a toll-free phone number by the smoker and access to Alere's WebCoach® online service and live chat; (4) self help print materials (i.e., "Quit Guide"); (5) tailored motivational emails and/or personal interactive text messages sent throughout the quitting process; and (6) up to 2 weeks of free NRT (patch or gum) for eligible smokers. The quitline also can provide materials for family members to help them support the smoker's quit attempt.

One treatment group will only receive the Specialized Quitline: Very low-income smokers are different from other smokers in important ways not always addressed by standard quitline services. As summarized in Table 2, these differences dictate modifications to counseling protocols, content and personnel. The research team and Alere staff will create and pre-test custom protocols, scripts, prompts and other content to maximize intervention relevance and acceptability to very low-income smokers. RIU coaches who will be delivering the Specialized Quitline services will receive training from clinical quitline staff, the research team and 2-1-1 staff who have extensive experience with the target population. Focus areas for training and distinctive content and protocol for the Specialized Quitline include:

- Health Literacy
- Abstract vs. concrete language
- Lived experience
- Resource constraints.
- Future orientation.
- Getting cigarettes.

- Living situation
- Phone/online access.

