The remaining two treatment groups will receive either the Standard or Specialized Quitlines with a Navigator. Navigators will: (1) identify and assess smokers' needs, including the reasons they called 2-1-1; (2) jointly generate solutions to address the needs; (3) develop plans to carry out the solutions, including; (4) help prioritize among multiple needs; (5) identify community resources that could help solve the problem; (6) determine eligibility for services; (7) help smokers access available resources by scheduling appointments and provide appointment reminders; (8) prepare smokers to interact with service agencies and/or act as an advocate on their behalf; (9) provide instrumental support such as arranging transportation; (10) actively intervene to resolve barriers to basic needs solutions; (11) oversee follow-up of problem solving actions; and (12) review progress made towards resolving unmet basic needs and adapt solutions accordingly.

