The benefits of this study far outweigh the minimal risks of participation. Little published research to date has examined the relative effect of unmet basic needs navigation intervention on smokers' ability to complete quitline counseling, and successfully abstain from smoking for 7 or more days at 3 and 6 months follow-up. If the addition of the basic needs navigator's support significantly improves cessation rates of quitline clients, such supports could become integrated into standard quitline training and service.

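### Aim 3 asks for each condition's own cost per quitter, which is not the cost of an extra quit, and it leaves open whether navigator costs count

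*Protocol*

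**What the plan says.** Aim 3 (Protocol section 1.4) sets out to "Conduct scalability and economic evaluations to assess the sustainability of the study's referral and intervention approaches". It has one research question, to be answered by study group: "What are the costs and benefits of each study condition per Quitline referral, per smoker interaction with the Quitline", and then "per successful quitter from the perspective of Quitline funders and providers". No condition is named as the comparator.

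The SAP describes analyses for Aims 1 and 2 and gives the sample size rationale (section 1.23). It has nothing on Aim 3: no cost items, no incremental ratio and no second perspective. Protocol section 1.1 states that there is no separate protocol. In these two documents, the Aim 3 question is therefore the only specification of the economic analysis.

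Three other places bear on the point:

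- Section 1.13 gives the control group the standard quitline alone. Of the navigator arms it says "The remaining two treatment groups will receive either the Standard or Specialized Quitlines with a Navigator". Among other tasks, navigators "provide instrumental support such as arranging transportation".
- Section 1.21 names the decision that the trial could inform for navigation: if it raises cessation rates, "such supports could become integrated into standard quitline training and service".
- The Aim 2 paragraph of the SAP takes the standard quitline without a navigator as referent for quit rates and uses everyone randomised as denominator. Nothing carries that contrast over to costs.

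**The concern.** The decision in view is whether to add something to a standard quitline that already exists. The figure that informs it is the extra cost of the addition divided by the extra quits it brings. A condition's own cost per quitter answers a different question, because it credits the arm with quits that the standard service would have been expected to produce as well.

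The perspective is a second, separate problem. Navigation is part of two of the four conditions, yet it is described as a service alongside the quitline, and the documents do not say who pays for it. If costs are limited to those borne by the quitline, navigator time and expenses could drop out of the numerator while the quits they help to produce stay in the denominator. Both problems bear on the sustainability conclusion. Neither touches the primary cessation outcome.

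**Working it through.** The documents give no cost or cost-per-quitter figure, so there is none to reproduce. The check uses the SAP's planning quit rates with assumed costs.

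**Inputs**

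- From SAP section 1.23: 500 per group, total quit rate 10%, 5-point difference between the combined arm and control, odds ratio 1.8.
- Planning rates: taking 10% as the mean of the two arms gives p0 = 7.5% (control) and p1 = 12.5% (combined). Their odds ratio is (0.125/0.875)/(0.075/0.925) = 1.76, consistent with 1.8. Solving for exactly 1.8 gives 7.41% and 12.59%.
- Assumed, because the documents give no costs: standard quitline C0 = 100 units per participant, with 50 to 400 units added in the combined arm (C1 = C0 + added).

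**Step 1: whose quits are counted.** Control: 500 × 0.075 = 37.5. Combined: 500 × 0.125 = 62.5. Extra: 62.5 − 37.5 = 25. So 37.5/62.5 = 60% of the combined arm's quits are expected under standard service.

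**Step 2: average against incremental.** Average = C1/p1. Incremental = (C1 − C0)/(p1 − p0). The control average is 100/0.075 = 1,333.

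| Added cost | Average, combined arm | Incremental | Incremental ÷ average |
|---|---|---|---|
| 50 | 150/0.125 = 1,200 | 50/0.05 = 1,000 | 0.83 |
| 100 | 200/0.125 = 1,600 | 100/0.05 = 2,000 | 1.25 |
| 200 | 300/0.125 = 2,400 | 200/0.05 = 4,000 | 1.67 |
| 400 | 500/0.125 = 4,000 | 400/0.05 = 8,000 | 2.0 |

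**Step 3: where the direction changes.** The incremental figure exceeds the average when (C1 − C0)/(p1 − p0) > C1/p1, which simplifies to C1/C0 > p1/p0 = 12.5/7.5 = 1.67. At an added cost of about 67 the two are equal, at 1,333.

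**Step 4: the perspective.** If all added cost is left out, the combined arm shows 100/0.125 = 800 per quitter against 1,333 for control. That is 1 − 800/1,333 = 40% lower, whatever navigation costs. This is the extreme case, since any added cost of specialised coaching would presumably still count as a quitline cost. A partial case: of 200 added, suppose 150 is navigator cost and is left out. The average becomes 150/0.125 = 1,200 instead of 2,400, and the incremental figure 50/0.05 = 1,000 instead of 4,000. The comparison of averages with control (1,333) then reverses.

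**Step 5: non-respondents counted as smokers.** If the planning rates apply to the 60% expected to be reached, the rates over all randomised are 0.6 × 7.5% = 4.5% and 0.6 × 12.5% = 7.5%. Their ratio is still 1.67, so the threshold does not move. With 200 added, the average is 300/0.075 = 4,000 and the incremental figure is 200/0.03 = 6,667.

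**The case against.** The strongest reply is that a research question is not an analysis specification. Aim 2 is also phrased by study group, yet the SAP goes on to compare groups with a referent. An incremental comparison is therefore unspecified, not ruled out, and it follows from arm totals if costs are captured. That is fair, but for Aim 3 no SAP text supplies the comparison, and following the question as written yields only per-arm figures.

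A second reply is that average cost per quitter for a stated payer is a legitimate budget figure. It is, and it should stay as description. It does not price the addition.

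Third, the reference to each study condition can be read to include navigation, and section 1.21 foresees navigation being integrated into the quitline, where its funder would count the cost. That stands too. Omission of navigator costs is a possibility left open, not something the plan states.

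A reader might also infer four stronger things that the documents do not support:

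- *The average always understates the cost of an extra quit.* Below a cost ratio of 1.67 it overstates it.
- *Averaging by itself favours the most intensive arm.* With full costs and 200 added, the averages are 2,400 for the combined arm and 1,333 for control, which favours control.
- *The navigator arms would look almost free.* Their quitline costs still count.
- *The trial can remove quits that would have occurred with no help at all.* Every arm receives a quitline, so only quits additional to the standard quitline can be estimated.

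**Conclusion.** The point holds as a gap in Aim 3 that should be closed. The figure asked for is not the cost of an extra quit, and it is unclear whether navigator costs belong in it. Over the assumed range of added cost (50 to 400 per 100 of standard cost), the incremental figure runs from 0.83 to 2.0 times the combined arm's average. Leaving out all added cost would put that arm 40% below control per quitter.

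The 60% share and the 1.67 threshold rest on the SAP's planning rates, with 10% taken as the mean of the two extreme arms. All cost figures are illustrative. The SAP gives no planning rates for the two arms with a single enhancement, so no size is given for them.

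**What to change.** Add to Aim 3, and to the SAP, the incremental cost per additional quitter for each of the three enhanced conditions against the standard quitline without a navigator. Calculate it over all randomised participants with the Aim 2 quit definition. State that navigator time and expenses are part of the cost of the two navigator conditions, and report a quitline-only version alongside. Keep the per-condition averages as description.

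The cost is one further calculation on quit counts that Aim 2 already produces. The SAP already plans to use the number of navigator contacts in its dose analysis, but time and expenses must be confirmed as recorded, and the documents do not say who pays for them. The enhanced arms' figures may look less favourable. The text should also say that the result concerns quits beyond those under the standard quitline, since no arm lacks one.
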